4.1 General Principles

The statistical evaluation will be performed by using the software package SAS version 9.4 (SAS Institute Inc., Cary, NC, USA) for all outputs assigned for publication, or R (version 4.1.0 [2021-05-18]) or higher for exploratory analysis.

The creation of TLFs will follow the standard as described in RD-SOP-1215.

Descriptive analysis of the data will be performed using summary statistics for categorical and quantitative (continuous) data. Continuous data will be described by the number of non-missing values, median, mean, standard deviation, minimum, and maximum as well as lower and upper quartiles. Frequency tables will be generated for categorical data.

Time-to-event analyses, and other model-based analyses, will be described in detail in subsequent sections.

4.2 Handling of Lost to Follow Up and Premature Discontinuation

Lost to follow-up or withdrawal of consent for study observations will result in the patient being censored for all time-to-event endpoints. Censoring times and status can be accommodated using either Kaplan-Meier methodology or Cox Proportional Hazards models, as detailed in later sections. Censoring details for each endpoint will be given in [section 6](#).

4.3 Handling of Missing Data

4.3.1 Baseline Data

No imputation of missing information will be applied except for partial dates with missing day only. These dates will be imputed to either first day of month, or first dose date if it falls in the same month.

Dates with month or year missing in addition to day will remain missing. This rule affects dates used in the analysis of patient and disease characteristics: dates of initial disease diagnosis and locally advanced/metastatic disease; dates of radiation therapy used to calculate duration of most recent radiotherapy.

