 - ✓ Cohorts containing at least clinical data allowing to assess the efficacy of the treatment and the main prognostic factors as follows:
 - Diagnosis and stage of the disease (locally advanced or metastatic),
 - Type of treatments (chemotherapy, radiotherapy, surgery: mutilating yes/no and date of the initiation or of the procedure,
 - Death and date,
 - Localization of the tumor (axis versus limb),
 - Size of the tumor (< 5 cm versus > 5 cm).
- Exclusion criteria:
 - ✓ Databases not containing patients with locally advanced or metastatic IFS,

- ✓ Medico-administrative databases or absence of data allowing the assessment of the efficacy of the treatment and main prognostic factors, or high rate of missing data (>10% on outcome and >25% on covariates),
 - The use of these databases, especially medico-administrative databases, is not feasible because of missing data and the limited information available on the clinical, biological, diagnostic and treatment data, notably for rare diseases like IFS. These limitations would be an issue for the prognostic, outcomes and selection criteria of patients.
- ✓ Cohorts with retrospective enrollment and case report,
 - Cohorts with retrospective enrollment or case report are subject to a greater risk of selection bias than those with prospective enrollment and with retrospective and prospective data collection, given that all patients who should have been considered to be included might have not been included a posteriori.
- ✓ Cohorts with prospective enrollment for which all patients were included before 2000,
 - There is a risk of classification bias for cohorts constituted before 2000 because of the evolution of the histological and molecular diagnosis of IFS (see details in the inclusion criteria).

Based on a preliminary search of databases and the selection criteria described above, in addition to the database of the *Institut Curie* which is the only database confirmed, the following data sources are theoretically eligible to be used to constitute (an) external historical control cohort(s) for the present study:

- Databases found in the literature (preliminary search that will be completed by the SLR):
 - ✓ Database from the European pediatric Soft tissue Sarcoma Study Group (EpSSG, a consortium housed in the University of Padua, Italy, European data),
 - ✓ Database from the *Cooperative Weichteilsarkom Studiengruppe* (CWS, Germany).
- Commercial databases with electronic medical data:

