9.7.2 Adjustment methodology

Patients who received larotrectinib in the SCOUT trial will likely differ in various underlying characteristics from those who are recorded in the external historical control cohort(s). These characteristics are listed above as potential confounders (See [Section 9.3.4](#)). The analyses will need to be adjusted for these patient characteristics to avoid biased results.

An adjustment methodology using a propensity score will be employed to reduce the effects of measured confounding variables in the interpretation of the treatment effect (larotrectinib versus historical group). A propensity score can be seen as an overall “balancing score”, that is calculated for each patient based on his or her measured underlying characteristics.

The propensity score will be obtained from a logistic regression model with dependent variable: larotrectinib group (yes/no). Covariates will be taken from the list of potential baseline confounders above (see [Section 9.3.4](#)). The predicted probabilities of receiving larotrectinib from this logistic regression model will form the propensity scores for each patient.

The most widely used propensity score is 1:1 matching, which involves selecting treated and control patients without replacement to form matched pairs. However, this typically requires a larger group of control patients than within the treated group, so that each treated patient can find a satisfactory matching control.

Because cases of IFS are exceedingly rare, resulting in small sample sizes, we favor IPTW as it is easy to implement and retains data from all patients (it does not discard the unmatched patients), which

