4.6 Definition of Derived Variables and Subgroups

A subgroup analysis will be performed on the primary endpoint for patients who take larotrectinib as second-line therapy or are treated with second-line or higher systemic therapy in the external historical cohorts. A similar subgroup analysis will be conducted for comparing first line Larotrectinib patients versus external controls taking at least 1 line of therapy. This is described fully in [section 6.2.5](#).

5. Analysis Sets

All analyses will be performed on the Full Analysis Set (FAS), comprising patients in the SCOUT trial, or the pooled population of Institut Curie and CWS.

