Two studies explored the impact of tumor size on clinical outcomes (Orbach 2010, Sparber Sauer 2020). Both studies concluded that tumor size (≤ 5 cm, > 5 cm) did not have an impact on EFS. Furthermore, the Orbach [2010] study did not find tumor size to be a prognostic factor of OS. As tumor size factors into IRS group stage (IRSG), tumor size will only contribute indirectly to the propensity score through IRSG.

Age

The SLR did not uncover any evidence of age having a statistically significant prognostic value on EFS and OS, probably due to small sample sizes. However, age will be retained as a prognostic factor due to the clinical importance of the covariate.

Time from locally advanced/metastatic disease diagnosis to initiation of larotrectinib (SCOUT) or first line of chemotherapy (external cohorts)

Based on the SLR, no study investigated how time from diagnosis to initiation of therapy affects clinical outcomes. Time from locally advanced/metastatic disease to initiation of treatment will be added to the core subset, acknowledging that there will likely be an initial imbalance on lines of therapy between treatment groups. Line of therapy will be substituted by elapsed time from locally advanced/metastatic disease in the PS model.

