6.2.2 Inverse Probability of Treatment Weighting (IPTW)

Patients who received larotrectinib in the SCOUT trial will likely differ in various underlying characteristics from those who are recorded in the external historical control cohorts. These characteristics are listed above as potential confounders (See [sections 6.1.2](#) and [6.1.4](#)). The analyses will need to be adjusted for these patient characteristics to avoid biased results.

An adjustment methodology using a PS will be employed to reduce the effects of measured confounding variables in the interpretation of the treatment effect (larotrectinib *versus* external historical group). A PS can be seen as an overall “balancing score”, that is calculated for each patient based on his or her measured underlying characteristics.

The PS will be obtained from a logistic regression model with dependent variable: larotrectinib group (yes/no). Covariates will be taken from the list of potential baseline confounders above. The predicted probabilities of receiving larotrectinib from this logistic regression model will form the PS for each patient. Example SAS code is as follows:

```
proc logistic data=temp;
class cat1 cat2 ... / param=ref;
model tx (event = "Laro") = cat1 cat2 var1 var2 ...;
output out=temp2 pred=propensity;
run;
```

where all categorical variables appear in the `class` statement in addition to the `model` statement. Predicted probabilities in the code example above appear in `temp2`.

Therefore, the weight assigned to each patient is the inverse probability of being in a certain group conditioning on these baseline covariates. For larotrectinib patients, this is the reciprocal of the PS, while for external comparator patients this is the reciprocal of one minus the PS. These weights are stabilized by multiplying by the marginal probability of treatment that was actually received, which avoids very large weights being assigned to larotrectinib patients with a very low PS or to comparator patients with a PS close to 1.

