The selection of covariates for retention in the logistic regression model for the PS will be considered. Brookhart et al [3] showed in simulations that: (1) including a variable in the PS model related only to survival but not to treatment group decreased the variance of the treatment effect without affecting bias; (2) failure to include a true confounder (i.e. related to both treatment group and survival) led to a biased estimator; (3) the inclusion of a variable related only to treatment group increased the variance of the treatment effect without altering bias. Similar results were reported by Andrillon, Pirracchio and Chevret [4], in small samples, who confirmed that matching on a PS model including instrument variables (associated with treatment allocation) increased the bias of the estimated treatment effect compared to matching on a prognostic model or on the true confounder model.

Two PS models will be considered:

1. **SLR model:** The core subset of variables in [section 6.1.4](#), comprising the prognostic factors identified by the SLR (, IRS group, age) and time from locally advanced/metastatic disease diagnosis to initiation of treatment.
2. **Full model:** All covariates in [1] and additional covariates listed in [section 6.1.2](#):
 - a. Additional demographic variables: sex;
 - b. Additional covariates on disease history: time from initial diagnosis to first dose of treatment tumor location;
 - c. Covariates on treatment-related information: prior surgical treatments for cancer, prior radiation treatment for cancer, prior systemic treatments.

The SLR only identified IRS group as a significant prognostic factor, and we have augmented the SLR model above with age (due to its clinical importance) and locally advanced versus metastatic disease stage (expert consensus on its likely significance despite lack of data). The failure of the SLR to identify other prognostic factors may in part be explained by the small sample sizes limiting the

power of those studies referred to in the report. Notwithstanding these data deficiencies, it does seem unlikely that the analysis could be biased by unmeasured confounders. However, this will be explored as detailed in [section 6.5](#) to allay any concerns. Balance metrics presented in the following section will help to discriminate between these two approaches for the PS model.

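### Baseline dates with an unknown month stay missing, so such patients would by default get no propensity weight and leave the weighted primary analysis

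*SAP*

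**What the plan says.** SAP 4.3.1 sets the rule for baseline data: "No imputation of missing information will be applied except for partial dates with missing day only". It continues: "Dates with month or year missing in addition to day will remain missing". The same section names the dates of initial diagnosis and of locally advanced/metastatic disease among those affected.

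These dates feed the PS models in SAP 6.1.4 and 6.2.2:

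- The SLR model uses IRS group, age, and time from locally advanced/metastatic diagnosis to start of treatment. On the last of these, SAP 6.1.4 says: "Line of therapy will be substituted by elapsed time from locally advanced/metastatic disease in the PS model".
- The Full model adds sex, time from initial diagnosis, tumor location, and "prior surgical treatments for cancer, prior radiation treatment for cancer, prior systemic treatments".

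SAP 6.2.2 describes how the scores arise: "The predicted probabilities of receiving larotrectinib from this logistic regression model will form the PS for each patient". The example code has no missing category or missing indicator.

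SAP section 5 states: "All analyses will be performed on the Full Analysis Set (FAS"). The FAS definition in SAP 5.1 sets no condition on complete covariates. Protocol 9.7 had left the methods for missing data to the SAP.

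**The concern.** A patient with no value for a PS covariate has no predicted probability and so no weight. That patient cannot enter the weighted Kaplan-Meier curves, the weighted log-rank test or the weighted Cox model of SAP 6.2.4. The same weights are reused for the secondary and exploratory endpoints (SAP 6.3), so the loss would carry over to them.

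Three things are at stake.

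- **Selection.** If patients with incomplete dates differ in prognosis, deleting them changes the population to which the weighted hazard ratio applies. The exposed covariate is an important one. It stands in for line of therapy, and Table 2 in SAP section 7 shows 63% of larotrectinib patients but 19% of controls at second line or higher.
- **Model choice.** SAP 6.2.3 chooses between the SLR and Full models on standardized differences and overlap coefficients. If the two models are fitted to different patients, those metrics differ partly because the samples differ.
- **Comparison of weighted and unweighted results.** SAP 6.2.4 overlays both sets of curves on one plot. A gap between them could then reflect deleted patients as well as weighting.

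**Working it through.** **Does the text lead to deletion?**

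1. SAP 4.3.1 leaves a date missing when the month is unknown, and it names both diagnosis dates.
2. SAP 6.1.4 and 6.2.2 build time from advanced disease (both models) and time from initial diagnosis (Full model) from those dates.
3. SAP 6.2.2 takes each weight from one logistic regression on all listed covariates. No section gives another rule for an incomplete record.
4. Such a record therefore has no PS and no weight. The SAP does not say this; it is the default behavior of the specified model.
5. The unweighted Kaplan-Meier and Cox analyses need no PS and keep every patient.

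**Which covariates are exposed?** Age and disease stage are eligibility items (Protocol 9.2.3.2; SAP 5.1.1). IRS group in SCOUT is derived from disease status (SAP 6.1.4). Tumor localization is a required variable for a control source (Protocol 9.2.3.1). The main exposure is therefore the two date-based times.

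**Size, by the SAP's own power formula (section 4).**

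Power = Φ( √(k·m)·|HR − 1| / (k·HR + 1) − 1.96 ), with m = n1·pE + n2·pC and k = n1/n2.

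Inputs from SAP section 4: n1 = 49, n2 = 42, pE = 0.04, pC = 0.19, HR = 0.25, two-sided alpha 0.05.

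The plan's own figure first:

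- m = 49 × 0.04 + 42 × 0.19 = 1.96 + 7.98 = 9.94 events
- k = 49/42 = 1.167
- √(1.167 × 9.94) × 0.75 / (1.167 × 0.25 + 1) = 1.977
- Power = Φ(1.977 − 1.960) = 50.7%, which matches the stated 51%

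The limit of 62.9% with unlimited controls also reproduces.

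The documents report no missingness rate, so the losses below are assumptions, applied to controls only:

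| Controls lost | n1 v n2 | Expected events | Power |
|---|---|---|---|
| 0% | 49 v 42 | 9.94 | 50.7% |
| 10% | 49 v 37.8 | 9.14 | 49.6% |
| 25% | 49 v 31.5 | 7.95 | 47.5% |

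Each control lost removes 0.19 expected events. With complete covariates nothing is lost.

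**The case against.** The strongest reply is that no document shows any missing PS covariate. SAP 5.1 admits only controls who meet the eligibility criteria, and Protocol 9.2.3.2 asks for available information on tumor, therapies and outcomes. Protocol 9.8 describes iterative cleaning of the Institut Curie data. Table 2 in SAP section 7 classifies all 42 controls by line of therapy (34 + 8). The study is exploratory and has no formal hypothesis, and a change of about three points in nominal power alters no decision. The SAP does state a rule, namely no imputation.

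Much of this stands. It shows that the problem may be small. It does not settle what happens to a patient with an unknown month, because the eligibility criterion names no date and no PS covariate.

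A reader might also infer four stronger things, which the documents do not support:

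- **That the FAS is broken.** Its definition is intact and the unweighted analyses use all of it. Only the commitment to run every analysis on it fails.
- **That the reason for choosing IPTW is defeated.** Protocol 9.7.2 says IPTW "retains data from all patients (it does not discard the unmatched patients"). This contrasts IPTW with 1:1 matching, and PS matching would lose the same incomplete patients. Ease of use and estimation of the average treatment effect are further stated reasons.
- **That only about 18 controls would remain.** Protocol 9.2.3.1 excludes sources with a "high rate of missing data (>10% on outcome and >25% on covariates"). Compounding 25% over three covariates gives 42 × 0.75³ = 17.7 controls and power of about 40%. But 25% is a ceiling for accepting a source and does not estimate missingness. Age and stage are eligibility items, so independent 25% gaps in all three covariates are not credible.
- **That losses fall mainly on controls.** Protocol 9.9 contrasts a closely monitored trial with possibly real-world controls, which makes this plausible. No document shows it.

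**Conclusion.** The point holds as a defect in how the weighted analysis is specified. The no-imputation rule, applied to dates that build PS covariates, makes the weighted primary analysis complete-case by default. That conflicts with the commitment to analyze the FAS, and it can leave the SLR and Full models compared on different patients.

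The size is unknown. If 10% to 25% of controls were lost, nominal power would fall from 50.7% to between 49.6% and 47.5%, a loss of about 1 to 3 points. Power is therefore the lesser issue; possible selection and the non-comparable model choice come first. The conclusion rests on the default handling of missing covariates in logistic regression and on at least one patient lacking a PS covariate. If none does, a sentence saying so closes the point.

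**What to change.** 1. Report the number of FAS patients lacking each PS covariate, separately for SCOUT, Institut Curie and CWS.
2. Where the year of a diagnosis date is known, impute the month within the bounds set by the diagnosis and index dates.
3. If PS covariates are still missing, use a simple multiple imputation based on arm and baseline covariates. State whether the outcome is included and why. Repeat the imputation within each bootstrap resample so that the confidence interval reflects it. Keep the complete-case analysis as a sensitivity analysis.
4. Compute the standardized differences and overlap coefficients for the SLR and Full models on the same patients.

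This needs no new data and modest programming. The drawback is that an imputation model at n = 49 + 42 = 91 must be kept simple, which is why the complete-case analysis should be retained as a check.

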4.3.2 Time to Event Data

No imputation will be performed for missing tumor response evaluations or dates.

The last known alive date (LKAD) is defined as the latest date indicating that the patient is still alive, among all available visit dates and other dates pertaining to a patient record (e.g. AEs) in the database. Partial documented dates (i.e. with day only missing) will be imputed using the first day of the month.

4.4 Interim Analyses and Data Monitoring

Interim analyses are not applicable to this retrospective observational externally-controlled study.

4.5 Data Rules

All documented therapies will be coded using the World Health Organization – Drug Dictionary (WHO-DD). Medical history and diagnoses will be coded using the latest Medical Dictionary for Regulatory Activities (MedDRA) version coding system.

Unless otherwise specified, baseline value is defined as last non-missing value on or prior to first dose of larotrectinib for the SCOUT study, or as last non-missing value on or prior to start date of chemotherapy (first line) for the external historical control cohorts.

Calculation of months is derived as: 1 month = 30.4375 days.

4.6 Definition of Derived Variables and Subgroups

A subgroup analysis will be performed on the primary endpoint for patients who take larotrectinib as second-line therapy or are treated with second-line or higher systemic therapy in the external historical cohorts. A similar subgroup analysis will be conducted for comparing first line Larotrectinib patients versus external controls taking at least 1 line of therapy. This is described fully in [section 6.2.5](#).

5. Analysis Sets

All analyses will be performed on the Full Analysis Set (FAS), comprising patients in the SCOUT trial, or the pooled population of Institut Curie and CWS.

5.1 Assignment of Analysis Sets

FAS

A patient will be included in the FAS if the patient has taken at least one dose of larotrectinib for SCOUT study, or has fulfilled the eligibility criteria for inclusion into the pooled external cohorts and has initiated chemotherapy.

All analyses detailed below will be repeated separately for two populations of FAS:

5.1.1 IFS Population

- Age \leq 21 years old
- Locally advanced or metastatic IFS
- Patients receiving
 - larotrectinib in the SCOUT trial, or
 - receiving at least one chemotherapy-based regimen in the external historical control cohorts.

5.1.2 IFS with documented NTRK gene fusion

- Age \leq 21 years old
- Locally advanced or metastatic IFS, which is NTRK fusion-positive.
- Patients receiving
 - larotrectinib in the SCOUT trial, or
 - receiving at least one chemotherapy-based regimen in the external historical control cohorts.

6. Statistical Methodology

A comparison of patients in the larotrectinib group with patients from the external historical control cohorts who received systemic therapy (chemotherapy-based regimen) will be conducted. The external cohorts will comprise a pooled database from the *Institut Curie* and *CWS*.

Patients who received larotrectinib in the SCOUT trial will likely differ in various underlying characteristics from those who are recorded in the historical control cohorts. These characteristics are listed as potential confounders in [section 6.1.2](#). A SLR was conducted to identify key covariates, as described in [section 6.1.3](#). The analyses will need to be adjusted for these patient characteristics to avoid biased results.

The Inverse Probability of Treatment Weighting [IPTW] method will be employed to reduce the effects of measured confounding variables in the interpretation of the treatment effect (larotrectinib *versus* control group). The propensity score (PS) is defined as the probability of a patient receiving larotrectinib conditional on his observed baseline covariates, and is obtained from a logistic regression model. In order to balance the analysis, a weight is assigned to each patient as the inverse probability of being in a certain group conditioning on these baseline covariates. Therefore, for larotrectinib patients, this is the reciprocal of the PS, while for external comparator patients this is the reciprocal of one minus the PS. If a patient has a higher probability of being in a group, it is considered as over-

represented, and therefore is given a lower weight. On the other hand, if the patient has a smaller probability of being in the group, it is considered as under-represented and is given a higher weight. Therefore, the statistical design of this study intends to use this weighting adjustment to remove sampling bias, though diagnostics to check whether balance has been achieved in baseline covariates between larotrectinib and external cohort groups will be performed.

